2.3. Randomization and Blinding

This is an open-label, single-arm study, and there is no blinding.

2.4. Data Monitoring Committee

There will be an Independent Data Monitoring Committee (iDMC) in this study. During the conduct of this study, an iDMC will review accumulating safety data on a regular basis to ensure the continuing safety of the study patients and to review any study conduct issues.

2.5. Sample Size and Power Considerations

This study is open-label and safety oriented in nature; therefore, no formal hypothesis testing is planned. The sample size for this study is not based on statistical considerations; hence, only descriptive statistics will be presented.

Based on the number of patients in the parent study (Study TEV50717-CNS-30080) approximately 45 patients who completed the parent study may enroll in this study.

2.6. Sequence of Planned Analyses

2.6.1. Planned Interim Analyses

There is no planned interim analysis of this study. Intermediate analysis may be performed for submission of a New Drug Application (NDA) or other purposes.

2.6.2. Final Analyses and Reporting

All analyses identified in this Statistical Analysis Plan will be performed after the end of study as defined in the study protocol.

This final version of the Statistical Analysis Plan and any corresponding amendments will be approved before database lock, in accordance to SOP GBP_RD_702 (Statistical Analysis Plan).

3. ANALYSIS SETS

3.1. Intent-to-Treat Analysis Set

The intent to treat (ITT) analysis set will include all enrolled patients, regardless of whether or not a patient took any TEV-50717. A patient is considered enrolled according to the status in the database.

Both safety and efficacy analyses will be based on the ITT analysis set.

3.2. Additional Analysis Set

No additional analysis set is planned.

In case of a patient who enrolled but without taking any investigational medicinal product (IMP), a safety analysis set will be considered as an exploratory analysis set for safety assessments. This safety analysis set will include all enrolled patients who receive at least 1 dose of IMP.

4. GENERAL ISSUES FOR DATA ANALYSIS

4.1. General

Descriptive statistics for continuous variables include number (n), mean, standard deviation (SD), standard error (SE), median, minimum, and maximum. Mean, SD and SE will not be presented if the number of patients in the analysis is less than 5 (n < 5).

Descriptive statistics for categorical variables include patient counts and percentages. Missing category will be displayed as appropriate.

4.2. Specification of Baseline Values

Generally, the baseline value is the last observed data before the first dose of IMP, unless otherwise noted. If the baseline assessments occur on the same day as the first dose of IMP, it is assumed that the patients follow study procedure and those baseline assessments will be used.

The baseline assessments that will need to be performed at the initial visit for the study will be determined at the time when the patient enrolls (baseline/day 1).

Day 1: Between 1 and <2 weeks after Study TV50717-CNS-30080 week 15 visit:

To reduce patient burden and not collect duplicate information, after obtaining appropriate informed consent/assent, relevant data collected in Study TV50717-CNS-30080 will be used to provide corresponding data in this open-label study baseline/day 1 visit.

Day 1 assessments for Study TV50717-CNS-30081 that are identical to Study TV50717-CNS-30080 week 15/week 16 visit assessments, whichever is most current, **do not** need to be repeated, except for orthostatic pulse rate and blood pressure, ECG, beta-human chorionic gonadotropin (β -HCG) tests in urine, the site-administered scales, and the patient/caregiver-completed questionnaires, which need to be repeated at day 1.

Any scales/questionnaires administered at the week 16 visit for Study TV50717-CNS-30080 do not need to be repeated if the day 1 visit of Study TV50717-CNS-30081 is the same day as the week 16 visit Study TV50717-CNS-30080. See protocol Section 3 for addition details for day 1 baseline assessments.

Day 1: Between 2 and <4 weeks after Study TV50717-CNS-30080 week 15 visit:

If, in the judgment of the investigator, the patient has *not* had any clinically significant change since the week 15 visit of Study TV50717-CNS-30080 in health, concomitant medications, clinical assessments, laboratories, ECGs, or non-medical interventions, the patient will undergo all day 1 assessments outlined in [Table 2](#), except hematology, chemistry, and urinalysis laboratories and urine drug screen, which can be carried over from Study TV50717-CNS-30080 week 15 or week 16 visit, whichever is more current.

If, in the judgment of the investigator, the patient has had a clinically significant change since the week 15 visit of Study TV50717-CNS-30080 in health, concomitant medications, clinical assessments, laboratories, ECGs, or non-medical interventions, the patient will undergo all screening procedures outlined in [Table 2](#). Patients who remain eligible for participation in the study will be asked to return for day 1 assessments.

Study drug will be dispensed at day 1 once all procedures and investigator-related assessments are completed and patient eligibility is confirmed.

4.3. Handling Withdrawals and Missing Data

For most variables, only observed data from the patients will be used in the statistical analyses, ie, there is no plan to impute missing data for these variables, unless otherwise specified.

Rules for handling missing items in efficacy and safety rating scales/questionnaire are presented in Section 6.2.2 and Section 8.

4.4. Study Days and Visits

Study days will be numbered relative to the baseline visit date. Day 1 is defined as the date of the baseline visit, and the first dose of the IMP will be taken the next morning (day 2). Days will be numbered relative to baseline (ie, ..., -2, -1, 1, 2, ...; day -1 being the day before the baseline visit).

For efficacy and safety by-visit analyses, data collected at post-baseline scheduled visits will be included using their scheduled visit.

Data collected at early termination and unscheduled visits will be included and assigned to a visit window as described below.

Table 4: Visit Windows for Early Termination Visit for Efficacy Assessments

Assessment ^a	Study Day Window	Scheduled Day	Scheduled Visit/Week
MD-CRS, CaGI-I, CGI-S	Day 2 - 143	Day 98	Week 14
	Day 144 - 234	Day 189	Week 27
	Day 235 - 325	Day 280	Week 40
	Day 326 - 374	Day 371	Week 53
	≥Day 375	Day 378	Week 54
UHDRS-TMS, UHDRS-TMC, UHDRS-TMD	Day 2 - 143	Day 98	Week 14
	Day 144 - 234	Day 189	Week 27
	Day 235 - 325	Day 280	Week 40
	≥Day 326	Day 371	Week 53
PEDI-CAT, COPM	Day 2 - 280	Day 189	Week 27
	≥Day 281	Day 371	Week 53

Statistical Analysis Plan

Uncontrolled Study—Dyskinesia in Cerebral Palsy

Study TV50717-CNS-30081

Assessment ^a	Study Day Window	Scheduled Day	Scheduled Visit/Week
CGI-I	Day 2 – 10	Day 7	Week 1
	Day 11 – 17	Day 14	Week 2
	Day 18 – 24	Day 21	Week 3
	Day 25 – 31	Day 28	Week 4
	Day 32 – 38	Day 35	Week 5
	Day 39 – 45	Day 42	Week 6
	Day 46 – 73	Day 49	Week 7
	Day 74 – 122	Day 98	Week 14
	Day 123 – 168	Day 147	Week 21
	Day 169 – 210	Day 189	Week 27
	Day 211 – 255	Day 231	Week 33
	Day 256 – 301	Day 280	Week 40
	Day 302 – 346	Day 322	Week 46
	Day 347 – 374	Day 371	Week 53
	Day 375 – 381	Day 378	Week 54
	≥Day 382	Day 385	Week 55

^aMD-CRS=Movement Disorder-Childhood Rating Scale; CaGI-I=Caregiver Global Impression of Improvement; CGI-I=Clinical Global Impression of Improvement; CGI-S=Clinical Global Impression of Severity; UHDRS-TMS=Unified Huntington's Disease Rating Scale—Total Motor Score; UHDRS-TMC=Unified Huntington's Disease Rating Scale—Total Maximal Chorea; UHDRS-TMD=Unified Huntington's Disease Rating Scale—Total Maximal Dystonia; PEDI-CAT=Pediatric Evaluation Disability Inventory—Computer Adapted Test; COPM=Canadian Occupational Performance Measure;

Table 5: Visit Windows for Early Termination Visit for Safety Assessments

Assessment ^a	Study Day Window	Scheduled Day	Scheduled Visit/Week
Vital signs and weight, 12-Lead ECG, C-SSRS, ESRS, CBCL-Syndrome Scale, ESS, Chemistry/hematology/urinalysis	Day 2 – 35	Day 21	Week 3
	Day 36 – 73	Day 49	Week 7
	Day 74 – 143	Day 98	Week 14
	Day 144 – 234	Day 189	Week 27
	Day 235 – 325	Day 280	Week 40
	Day 326 – 374	Day 371	Week 53
	≥Day 375	Day 378	Week 54
Physical examination, Height	Day 2 – 280	Day 189	Week 27
	≥Day 281	Day 371	Week 53

Assessment ^a	Study Day Window	Scheduled Day	Scheduled Visit/Week
Orthostatic Vital Signs	Day 2 – 234	Day 98	Week 14
	>Day 235	Day 371	Week 53
Neurological examination	Day 2 – 374	Day 371	Week 53
	≥Day 375	Day 378	Week 54
CBCL-full assessment	≥Day 2	Day 371	Week 53

^a CBCL=Child Behavior Checklist (for ages 6-18); C-SSRS=Columbia-Suicide Severity Rating Scale; ECG=electrocardiogram; ESRS=Extrapyramidal Symptom Rating Scale (subscale I and II); ESS =Epworth Sleepiness Scale (for children and adolescents);

After mapping the data to the analysis visits of unscheduled and early termination visits, the following rules will apply unless other handling is specified for a particular analysis:

- If there is a scheduled visit in the analysis window, the last non-missing scheduled visit will be selected.
- If there is no scheduled visit, but early termination visit, early termination visit will be selected.
- If there are no scheduled or early termination visits, the record closest to the planned assessment day will be selected for analysis.
- If there are no scheduled or early termination visits, and 2 records are equidistant from the scheduled day, then the later record will be selected.
- If a patient has no scheduled record or early termination/unscheduled visits in an analysis window, the patient will be considered missing at that visit.

For these analyses performed by time period, eg, adverse events, the following definitions will be used:

- Titration Period - from the first dose of treatment until the day of the week 7 visit. For patients discontinued before the week 7, the Titration Period is until the later of the last dose of treatment and the early termination visit.
- Maintenance Period - from the day after the week 7 visit until the day of the week 53 visit. If a patient enters the Maintenance Period but discontinues treatment early, the Maintenance Period is until the later of the last dose of treatment and the early termination visit.
- Overall Treatment Period - includes the Titration and the Maintenance Periods, if applicable.
- Follow-up Period - from the end of the Overall Treatment Period through the end of the study.

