Should a patient decide to withdraw after administration of TEV-50717, or should the investigator decide to withdraw the patient, all efforts will be made to complete and report all observations up to the time of withdrawal. A complete final evaluation at the time of the patient's withdrawal should be made and an explanation given as to why the patient is withdrawing or being withdrawn from TEV-50717.

For patients who withdraw prematurely, an ET visit should be conducted as soon as possible after the last dose of TEV-50717. All patients who discontinue early will have a follow-up telephone contact for safety evaluation 2 weeks after their ET visit; evaluations will be as described for the week 55 visit.

Patients experiencing an adverse event leading to discontinuation of TEV-50717, or experiencing any other adverse event, should have a single blood sample collected for the measurement of TEV-50717,  $\alpha$ -HTBZ and  $\beta$ -HTBZ concentrations, if possible. This should be done (at the discretion of the investigator) as soon as possible after the onset of the ongoing adverse event and within 48 hours after the last dose intake in the case of TEV-50717 discontinuation. To permit the assessment of a potential relationship of the adverse event and plasma concentration,

an estimate of the date and time of the last dose intake of study drug should be recorded along with the date and time of the sample collection. If the estimate of the dose intake cannot be established within a 2 hour window, then a blood sample should not be obtained.

The reason for and date of withdrawal from TEV-50717 and the reason for and date of withdrawal from the study must be recorded on the source documentation and transcribed to the case report form (CRF). If a patient withdraws consent, every attempt will be made to determine the reason. If the reason for withdrawal is an adverse event or a clinically significant abnormal laboratory test result, monitoring will be continued at the discretion of the investigator (eg, until the event has resolved or stabilized, until the patient is referred to the care of a health care professional, or until a determination of a cause unrelated to TEV-50717 or study procedure is made). The specific event or test result must be recorded on the source documentation and transcribed to the CRF.

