8.5. Clinical Laboratory Tests

Summary statistics for chemistry, hematology and coagulation, and urinalysis laboratory tests are assessed at screening and weeks 3, 7, 14, 27, 40, 53/ET, and 54/follow-up visits. Laboratory values and changes from baseline to week 53 will be presented.

A list of laboratory tests is included in Table 10 of the study protocol.

Shifts (below, within, and above the normal range) from baseline to each visit will be summarized using patient counts for all the laboratory tests as applicable. Only patients with both baseline and post-baseline assessments will be summarized in the shift tables.

Only central laboratory assessments will be summarized; local laboratory assessments will be listed. Values below the lower limit of quantification or above the upper limit of quantification will be assessed on a case-by-case basis if present in the data and discussed in the final blinded statistical data review meeting.

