8.14.2. ESRS II

The second subscale (ESRS II) is a 17-item questionnaire to evaluate parkinsonism and akathisia.

ESRS II consists of the following parts:

1. Tremor: scored on a 7-point item scale for 8 parts of the body. For each part of the body, frequency and amplitude are selected, assigning each one of the 8 items a score from 0=none to 6=severe. Therefore, the total score for tremor can ranged from 0 to 48.
2. Bradykinesia: scored on a 7-point item scale (0-6).
3. Gait and Posture: scored on a 7-point item scale (0-6).
4. Postural stability: scored on a 7-point item scale (0-6).
5. Rigidity: scored on a 7-point item scale (0-6) for 4 parts of the body. Therefore, the total score for rigidity can ranged from 0 to 24.
6. Expressive automatic movements: scored on a 7-point item scale (0-6).
7. Akathisia: scored on a 7-point item scale (0-6).

The total score of the 17 items can ranged from 0 to 102.

Total score will be the sum of the 17 items. Missing item will be replaced by the average of the remaining responses within each item.

Total score and total scores change from baseline will be summarized by time point, using descriptive statistics for continuous variables.

Data will be listed.

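### Under SAP 4.4 an early-termination score that follows a scheduled visit in the same window is displaced; for ESRS, ESS and possibly CBCL Syndrome no summary table then shows it

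*SAP*

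**What the plan says.** Protocol 4.3 asks for a full assessment when a patient stops: "A complete final evaluation at the time of the patient's withdrawal should be made". SAP 4.4 brings those data into the by-visit analyses: "Data collected at early termination and unscheduled visits will be included and assigned to a visit window as described below". Three statements then decide which record represents a patient in a window:

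- a scheduled record takes first place: "If there is a scheduled visit in the analysis window, the last non-missing scheduled visit will be selected"
- the ET record serves as the fallback: "If there is no scheduled visit, but early termination visit, early termination visit will be selected"
- both are defaults: "the following rules will apply unless other handling is specified for a particular analysis"

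One row of SAP Table 5 sets common windows for "Vital signs and weight, 12-Lead ECG, C-SSRS, ESRS, CBCL-Syndrome Scale, ESS, Chemistry/hematology/urinalysis". A separate row sends the full CBCL, from day 2 onwards, to Week 53.

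No other handling is specified for ESRS, ESS or CBCL Syndrome. SAP 8.14.2 on ESRS II reads: "Total score and total scores change from baseline will be summarized by time point, using descriptive statistics for continuous variables". SAP 8.14.1 (ESRS I), 8.13 (ESS) and 8.12.2 (CBCL Syndrome) take the same form. For laboratory data SAP 8.5 says: "Laboratory values and changes from baseline to week 53 will be presented", and adds shift tables by visit.

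**The concern.** Safety and tolerability is the primary objective, and ESRS, CBCL and ESS are three of its eight listed measures. Protocol 7.1.6 names no adverse events of special interest and relies on standardized scores to follow parkinsonism, behaviour change and sleepiness. A score taken when a patient stops is among the more informative of these.

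Take a patient with a Week 14 visit on day 98 and an ET visit on day 130. Both fall in the window for days 74 to 143. The Week 14 row carries the day 98 ESRS score, and the day 130 score appears only in a listing.

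The SAP closes this gap for comparable measures. Potentially clinically significant vital signs and ECG values are counted over all post-baseline visits including ET (8.1, 8.8, 8.9). Overall ECG interpretation uses the worst post-baseline finding (8.9), and C-SSRS has a shift to the worst category on treatment (8.11). ESRS, ESS and CBCL Syndrome have no equivalent.

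Laboratory values are exposed too. Protocol 9.6 promises a summary of potentially clinically significant laboratory values against predefined criteria, but the SAP gives criteria only for vital signs and ECG.

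**Working it through.** **Windows.** The scheduled days in SAP Table 5 are 21, 49, 98, 189, 280, 371 and 378. The midpoints of neighbouring days are 35, 73.5, 143.5, 234.5, 325.5 and 374.5. Rounded down, these reproduce the printed upper limits of 35, 73, 143, 234, 325 and 374.

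**Count.** Let the ET visit fall on any day from 2 to 370, which is 370 − 2 + 1 = 369 days. Assume every earlier scheduled visit took place on its nominal day with a non-missing score. The ET score is displaced when its day is later than the scheduled day but still inside the same window.

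| Window (days) | Scheduled day | ET days displaced | Days in window |
|---|---|---|---|
| 2–35 | 21 | 22–35: 14 | 34 |
| 36–73 | 49 | 50–73: 24 | 38 |
| 74–143 | 98 | 99–143: 45 | 70 |
| 144–234 | 189 | 190–234: 45 | 91 |
| 235–325 | 280 | 281–325: 45 | 91 |
| 326–370 | 371 | 0 | 45 |
| Total | | 173 | 369 |

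173/369 = 46.9%. The ET score is kept on the other 369 − 173 = 196 days (53.1%).

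**Sensitivity to visit timing.** Weeks 3 and 7 may run ±3 days and the maintenance visits ±7 days.
- All early: 17 + 27 + 52 + 52 + 52 = 200; 200/369 = 54.2%.
- All late: 11 + 21 + 38 + 38 + 38 = 146; 146/369 = 39.6%.

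**Patients.** The documents give no expected withdrawal rate, so 15% to 30% of 45, spread evenly over time, is an assumption.
- 15%: 45 × 0.15 = 6.75 withdrawals; 6.75 × 0.469 = 3.2 patients.
- 30%: 45 × 0.30 = 13.5 withdrawals; 13.5 × 0.469 = 6.3 patients.
- Across the timing range above these become 2.7 to 3.7 and 5.3 to 7.3.

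**CBCL.** The Competence Scale is scheduled after baseline only at Week 53/ET, and the full assessment maps to Week 53 from day 2 onwards. No earlier scheduled record competes, so 0 of 369 ET days are displaced. The ET CBCL also contains the Syndrome Scale (SAP Table 3, CBCL footnote). SAP 8.12.2 leaves Week 53/ET out of its list of Syndrome visits, and Table 5 does not say whether the ET Syndrome score follows the Syndrome windows (173/369) or the full-assessment window (0/369).

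**Efficacy scales (SAP Table 4).**
- Physician-rated MD-CRS and UHDRS, CaGI-I and CGI-S: days 99–143, 190–234 and 281–325; 45 + 45 + 45 = 135; 135/369 = 36.6%.
- PEDI-CAT and COPM: days 190–280; 91/369 = 24.7%.
- Centrally read MD-CRS, UHDRS-TMC and UHDRS-TMD: the scheduled post-baseline readings are at Weeks 27, 53/ET and 54 only (Protocol 6.1.1 and 6.1.6), so just days 190–234 compete; 45/369 = 12.2%.
- CGI-I has finer windows of its own and is not counted here.

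**Laboratory tests** share the Table 5 row, so the 173/369 count also applies to their by-visit tables.

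**The case against.** Preferring the on-schedule record in its own window is a defensible by-visit convention, and the plan does not leave stopping patients unreported. Investigators must review the scales for adverse events (Protocol 6 and 7.2). Treatment-emergent events, including those causing withdrawal, are tabulated (SAP 8.3). Withdrawals are summarized by reason (SAP 5.2), with a Kaplan-Meier analysis of time to discontinuation if more than 15% withdraw (SAP 9). The data are listed, and no hypothesis test depends on the rule. A patient withdrawn for parkinsonism would be counted among withdrawals for adverse events. All of this stands. These outputs report events, reasons and timing, however, and not the score at the point of stopping, on which Protocol 7.1.6 relies.

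Four stronger inferences are tempting, and the documents do not support them.

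1. *The status of everyone who stops vanishes from the tables.* The second selection rule keeps the ET record when the window holds no scheduled visit, which is 196 of 369 days and includes all of days 326 to 370.
2. *All of CBCL is lost.* Competence ET scores are always kept, and the Syndrome part is unresolved.
3. *All MD-CRS and UHDRS endpoints share the 37% figure.* The centrally read versions do not.
4. *The rule biases results towards good tolerability or efficacy.* The documents do not show how ET scores compare with the scheduled scores that displace them, and withdrawals may be unrelated to either. Later rows describe only those who stay because the analysis uses observed data. The day 130 patient is already counted at Week 14, and swapping in the ET value would not add that patient to later visits.

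**Conclusion.** The point holds in a limited form. For ESRS I and II and ESS, and for CBCL Syndrome if it follows the Syndrome windows, an ET score that comes after a scheduled visit in the same window reaches listings only. That covers 46.9% of possible ET days (about 40% to 54% with permitted visit timing), or roughly 3 to 6 of 45 patients.

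The percentages assume that all earlier scheduled visits took place with non-missing scores and that ET is equally likely on each of days 2 to 370. The patient count also assumes 15% to 30% withdrawal. The direction of any bias is unknown. The efficacy scales and by-visit laboratory tables are affected by the same rule, to the extents shown above. In a descriptive single-arm study this is a worthwhile, inexpensive improvement to the primary safety summaries, and not a must-fix error.

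**What to change.** Keep the by-visit rule in SAP 4.4, and:

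1. Add an end-of-treatment row to the ESRS, ESS, CBCL Syndrome, laboratory and efficacy-scale tables. Define it as each patient's last non-missing on-treatment assessment from scheduled, ET or unscheduled visits, and show change from baseline where the scale has one. The SAP's own treatment period already runs to the later of the last dose and the ET visit, so ET assessments qualify. For completers the row would normally hold Week 53, not the washout visit.
2. State which window the ET CBCL Syndrome score follows.
3. Optionally, add a worst-on-treatment row for ESRS, ESS and CBCL Syndrome, in line with what the SAP does for ECG interpretation and C-SSRS.

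The cost is a few lines of SAP text and some extra table rows. No new data are needed, and SAP 2.6.2 allows amendments up to database lock. With the first change, the number of ET days on which a completed ET assessment on these scales reaches no summary table falls from 173 of 369 to 0.

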### 9.3. Data Handling Conventions

For all variables, only the observed data from the patients will be used in the statistical analyses.

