1. STUDY OBJECTIVES

1.1. Primary and Secondary Study Objectives and Endpoints

The primary and secondary study objectives and endpoints are presented below in [Table 1](#).

Table 1: Primary and Secondary Study Objectives and Endpoints

Objectives	Measures/Endpoints
The primary objective of this study is to evaluate the safety and tolerability of long-term therapy with TEV-50717 in children and adolescents with dyskinesia in cerebral palsy (DCP).	
The safety measures/endpoints are as follows:
 
adverse eventsvital signschildren's C-SSRSECG parametersclinical laboratory parameters (hematology, serum chemistry, and urinalysis)ESRS (subscales I and II)CBCLESS
A secondary objective of this study is to evaluate the efficacy of long-term therapy with TEV-50717 in reducing the severity of DCP.	
The efficacy measures/endpoints are as follows:
 
MD-CRS part I total score (centrally read)MD-CRS part II total score (centrally read)MD-CRS part I total score (physician rated)MD-CRS part II total score (physician rated)MD-CRS Global Index (calculated from MD-CRS parts I and II total scores)CaGI-I (global, caregiver rated)CGI-I (global, physician rated)CGI-S (global, physician rated)PEDI-CAT (ADL, caregiver completed, content-balanced version)UHDRS-TMC (centrally read)UHDRS-TMD (centrally read)UHDRS-TMS (physician rated)

Objectives	Measures/Endpoints
	
• UHDRS-TMC (physician rated)• UHDRS-TMD (physician rated)• COPM (physician rated)

CaGI-I=Caregiver Global Impression of Improvement; CBCL=Child Behavior Checklist (for ages 6 to 18); CGI-I=Clinical Global Impression of Improvement; CGI-S=Clinical Global Impression of Severity; COPM=Canadian Occupational Performance Measure; C-SSRS=Columbia-Suicide Severity Rating Scale; DCP=dyskinesia in cerebral palsy; ECG=electrocardiogram; ESRS=Extrapyramidal Symptom Rating Scale (subscales I and II); ESS=Epworth Sleepiness Scale (for children and adolescents); MD-CRS=Movement Disorder-Childhood Rating Scale; PEDI-CAT=Pediatric Evaluation Disability Inventory-Computer Adapted Test; ADL=activities of daily living; UHDRS-TMC=Unified Huntington's Disease Rating Scale-Total Maximal Chorea; UHDRS-TMD=Unified Huntington's Disease Rating Scale-Total Maximal Dystonia; UHDRS-TMS=Unified Huntington's Disease Rating Scale-Total Motor Score.

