The MD-CRS Global Index is a global measure of the MD-CRS that consolidates the information from parts I and II using the method of weighted means of the 2 normalized indexes obtained from each part. The minimum score is 0 and the maximum score is 1.

The standardized/normalized score for each item of MD-CRS parts I and II with value X is calculated using the formula

$$X_{st} = \frac{X - X_{min}}{X_{max} - X_{min}}$$

where X_{max} is the maximum value for the score, and X_{min} is the minimum value for the score, or 4 and 0 respectively.

The normalized index for the scale, MD-CRS parts I or II, Index I or II, is calculated as the mean value of X_{st} .

The MD-CRS Global Index is the weighted mean of the normalized indexes for MD-CRS parts I and II using the formula:

$$\text{Global Index} = \frac{n_I \times \text{Index}_I + n_{II} \times \text{Index}_{II}}{n_I + n_{II}}$$

where n_I and n_{II} are the numbers of items in MD-CRS parts I and II respectively.

The actual values and change from baseline for the MD-CRS Part I, Part II and Global Index scores will be summarized.

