9. TOLERABILITY VARIABLES AND ANALYSIS

If more than 15% of the patients withdraw from the study before the end of the treatment period, the number of days until study discontinuation will be analyzed using Kaplan-Meier methodology with the ITT analysis set.

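### Efficacy is summarised only by visit on observed data, so the week 53 summary comes almost entirely from patients still in the study near week 53, and some early-termination scores drop out of the by-visit tables

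*SAP*

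**What the plan says.** The secondary objective (SAP 1.1) is to "evaluate the efficacy of long-term therapy with TEV-50717 in reducing the severity of DCP". SAP 6.1 assigns all efficacy analyses to the ITT set. SAP 4.3 says that, for most variables, "only observed data from the patients will be used in the statistical analyses", with no imputation unless otherwise specified; for efficacy, the exceptions concern missing items within a scale. Protocol 9.3 says the same for all variables: "only the observed data from the patients will be used in the statistical analyses".

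The output is descriptive by visit. For the main scale, SAP 6.2.2.1 says: "The actual values and change from baseline for the MD-CRS Part I, Part II and Global Index scores will be summarized". SAP 4.4 assigns ET and unscheduled records to windows by study day (Table 4). Within a window, a scheduled record takes precedence over an ET record. If the window is empty, the rule is: "If a patient has no scheduled record or early termination/unscheduled visits in an analysis window, the patient will be considered missing at that visit".

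After early stopping, Protocol 4.3 provides one ET visit and then a safety telephone contact, so no later efficacy is collected. Withdrawals are tabulated by reason (SAP 5.2). SAP 9 adds a Kaplan-Meier analysis of time to discontinuation: "If more than 15% of the patients withdraw from the study before the end of the treatment period". SAP 6 contains no last-value summary, model over visits or sensitivity analysis for efficacy.

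**The concern.** In a single-arm study with no inference, the size and durability of the mean change are what readers will take as the efficacy result. When each visit uses only those observed, the mean can improve from week 14 to week 53 because weaker responders have left, without any patient changing. The ITT label does not prevent this, because the number contributing can shrink at each visit.

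Leaving could plausibly be related to outcome. Protocol 4.3 allows withdrawal for adverse events or on request, and dosing is adjusted to CGI-I response and tolerability.

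Two filing rules add to this. A score taken when a patient leaves can be displaced by an earlier scheduled score in the same window. Centrally read scores, the only blinded ratings in an open-label study, can be filed under visits where nobody else has a central reading.

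**Working it through.** There is no sample-size calculation to reproduce. SAP 2.5 gives the number as "approximately 45 patients who completed the parent study may enroll in this study" and states: "The sample size for this study is not based on statistical considerations; hence, only descriptive statistics will be presented". The check therefore covers where ET scores go and what follows for week 53.

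**1. ET scores that reach week 53.** Treatment runs from day 2 to day 371, which is 370 days. The share of days on which an ET visit falls in the week 53 window is (371 − window start + 1)/370.
- MD-CRS, UHDRS, CaGI-I, CGI-S (from day 326): 46/370 = 12.4%
- PEDI-CAT, COPM (from day 281): 91/370 = 24.6%
- CGI-I (from day 347): 25/370 = 6.8%

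If stopping is spread evenly over treatment (an assumption), about 88%, 75% and 93% of early leavers with an ET visit have no week 53 value.

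**2. ET scores displaced by a scheduled visit.** For physician-rated MD-CRS with on-time visits at days 98, 189 and 280, the windows close at days 143, 234 and 325. ET visits on days 99-143, 190-234 and 281-325 share a window with a scheduled record. That is 45 + 45 + 45 = 135 of 370 days (36%).

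**3. Centrally read ET scores.** After day 1, central readings are scheduled at weeks 27, 53/ET and 54 only (Protocol 6.1.1 and 6.1.6). Table 4 does not separate central from physician ratings. It files ET records from days 2-143 under week 14 and from days 235-325 under week 40. That is 142 + 91 = 233 of 370 days (63%). Those central rows would hold only leavers or unscheduled records, and SAP 4.1 suppresses mean, SD and SE when n is below 5.

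**4. Effect on the week 53 mean change.** Let N = 45, k = number leaving, q = leavers' mean change as a fraction of stayers', and e = share of leavers whose ET score enters week 53. In units of the stayers' mean change:
- observed week 53 mean = (N − k + k·e·q)/(N − k + k·e)
- mean counting every leaver's outcome = (N − k + k·q)/N
- excess = first/second − 1

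The documents give no effect size or dropout rate, so k, q and e are assumptions. k = 7 is the smallest count above 15% of 45 (6.75); 9 and 14 are illustrative. With q = 0 the excess is N/(N − k(1 − e)) − 1:

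| Leavers | e = 0 | e = 12.4% (MD-CRS) | e = 24.6% (PEDI-CAT, COPM) |
|---|---|---|---|
| 7 | 45/38: 18% | 45/38.87: 16% | 45/39.72: 13% |
| 9 | 45/36: 25% | 45/37.12: 21% | 45/38.21: 18% |
| 14 | 45/31: 45% | 45/32.74: 37% | 45/34.44: 31% |

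With 7 leavers at half the stayers' benefit (q = 0.5) and e = 0, the two means are 1 and 41.5/45 = 0.922, an excess of 8%. With e = 12.4% they are 38.44/38.87 = 0.989 and 0.922, an excess of 7%. With q = 1 the excess is 0 throughout.

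**The case against.** Several points on the other side stand.

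- A reader might infer that week 53 comes only from patients who stayed on treatment. Table 4 does not support that: late ET scores enter week 53, most of all for PEDI-CAT and COPM.
- A reader might infer that leavers appear in no efficacy table. The first window runs from day 2 to 143 for MD-CRS, UHDRS, CaGI-I and CGI-S, and from day 2 to 280 for PEDI-CAT and COPM. Those tables can hold nearly every treated patient with a post-baseline score. What is absent is each patient's last value.
- Neither document names week 53 as the visit that answers the objective. It is the last on-treatment visit and the complete evaluation, so readers will tend to use it, but that is an inference.
- Outcome-related leaving is plausible, not shown. Protocol 4.3 does not list lack of efficacy as a reason, though it could lie behind a request to stop, and some exits under Appendix M are logistical. Leaving for intolerance inflates efficacy only if those patients also benefited less.
- Attrition will be visible through n per visit, withdrawal reasons and, if triggered, Kaplan-Meier. These show how many leave and when; they do not correct the efficacy mean.
- A last-value row has its own weakness. The ET visit takes place after the last dose with no stated limit, so off-drug scores could enter unless a cut-off is set.

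**Conclusion.** The point holds as a modest, inexpensive improvement. The planned tables do what the SAP says they do. The gap is that no efficacy summary shows each treated patient's last value, most early leavers will be absent from week 53, and some ET scores are displaced or filed where they have no comparators.

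For 7 of 45 leaving with zero benefit, week 53 would overstate the all-treated mean change by about 16% (evenly spread stopping) to 18% (no leaver reaching the window) for MD-CRS, and by about 13% for PEDI-CAT and COPM with evenly spread stopping. The excess grows with more leavers and vanishes if leavers respond as well as stayers. These figures rest on assumed dropout, response and timing. The 15% in SAP 9 triggers an analysis and is not a forecast of dropout. It would go too far to say that the week 53 result will be biased; the documents support only that it would favour the drug if leavers did worse. Efficacy here is secondary, uncontrolled and non-inferential, which limits the weight of the point.

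**What to change.** In SAP 6.2:
1. Keep the by-visit tables unchanged and add one supportive row per efficacy endpoint, named last treatment-period assessment. It uses each treated patient's latest scheduled, unscheduled or ET record by date through week 53, not week 54.
2. State beforehand a maximum gap between last dose and assessment. A record beyond it is excluded as off-drug, and the latest earlier eligible record is used.
3. Apply the row separately to centrally read and physician-rated scores.
4. At each visit show n and, for change scores, the day 1 mean of the same contributors. CGI-I and CaGI-I have no day 1 value, so n suffices there.
5. State that week 53 alone describes patients who remained in the study and is read together with the new row.
6. Record the addition in SAP Section 11.

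The cost is SAP wording and one row per table, from data already collected at the ET visit; no new assessments or patients are needed. The downside is that the row mixes treatment durations, including patients who left during titration. It is therefore not an estimate of one-year efficacy: it is read beside week 53 and does not replace it.
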